6.3.1.2. Coding of Reported Terms

All AE terms will be coded in the database using the latest version of MedDRA coding dictionary. AEs will be graded using the National Cancer Institute Common Terminology Criteria for Adverse Events (NCI CTCAE).

All tables will show the AE preferred terms grouped into system organ class. Subject listings will also show the reported terms (verbatim). Any other coding levels will only be shown in a listing summarizing coding unless explicitly mentioned otherwise.

6.3.1.3. Allocation of Adverse Events to Analysis Periods

All AEs will be placed into analysis periods considering their start date, aiming to report the incidence of these events only in the analysis period during which they started.

The general rule for allocation of AEs to analysis periods follows:

$$\text{Analysis period start date} \leq \text{AE start date} \leq \text{analysis period end date}$$

If the start date of an AE is missing or incomplete to a level preventing a clear allocation of the AE to one single analysis period and no flag indicating timing relative to study medication is available, a worst-case consideration (see below) will be done aiming to allocate the AE to one single analysis period, if possible. When a worst-case consideration is needed, the end date of the AE, if and as available, should also be considered; if such AEs clearly end on a given point, this will exclude the possibility to allocate the AE to an analysis period after that point.

- An AE which according to the available information of its start date could belong to the screening as well as to the treatment analysis period will only be placed in the treatment period.
- An AE with a missing start date will be allocated to the treatment period unless the “Prior to First GLPG3970/Placebo Treatment= “Yes”.

6.3.1.4. Treatment Relatedness

Following the guideline ICH-E3 Structure and Content of Clinical Study Reports (Step 4 Version), the originally reported relatedness to IP of an AE will be dichotomized as follows:

- *Not IP related*: all non-missing weaker levels of relatedness than ‘possibly drug related’.
- *IP related*: ‘possibly drug related’ and all stronger levels of relatedness (this class also includes any missing drug relatedness, as a worst-case consideration).

Only this dichotomized relatedness will be used in tables and can apply to different IPs when relatedness has been collected separately per IP; relatedness as originally reported will only be listed.

6.3.1.5. Worst-Case Selections

When cross-tabulating AE preferred terms versus an AE attribute (like intensity), only the worst-case within each same preferred term, same subject and same analysis period will be considered, i.e. when the same subject has more than once the same AE preferred term reported in the same treatment group, the subject will be counted only once and will be shown under the worst outcome (like the worst intensity for that AE in the concerned treatment period).

The severity grade of events for which the investigator did not record severity will be categorized as “missing” for tabular summaries and data listings. The missing category will be presented last in summary presentation.

6.3.1.6. Calculation of Relative Days and Duration

For each newly reported event, and reported worsening or improvement of an existing event, the start day in the study (the day of the AE start date relative to the date of first IP administration), the start day in the analysis period, and the duration (in days) will be calculated. In addition, the relative day and duration will be derived for the entire event; that is, the full evolution of the event, including the initial reporting and all subsequent worsening and/or improvement.

Relative days and durations will only be listed.

See Section [4.3.1](#) for the calculation of relative days.

6.3.1.7. Events of Special Interest

Not applicable.

6.3.1.8. Presentation of Results

The analysis will focus on AEs reported during the treatment period. AEs reported during the screening period will only be listed.

All AEs tables will show the number of subjects with TEAEs.

AEs which are not treatment-emergent will only be listed.

A summary table will be provided, showing the number (percent) of subjects with at least one:

- TEAE,
- IP-related TEAE,
- Serious TEAE,
- TEAE leading to death,
- TEAEs by worst intensity (CTCAE Toxicity Grade),
- TEAE leading to IP discontinuation.

The AE terms will be presented sorted in descending order of frequency, prioritizing the GLPG3970 treatment group and then for placebo, first by system organ class, then by preferred term, and then alphabetically.

Frequency tabulations, by system organ class and preferred term, of the number (percent) of subjects with a TEAE will be presented. Similar tables will be provided by worst intensity, and for IP-related TEAEs, grade 3-4-5 TEAEs, serious TEAEs and TEAEs leading to IP discontinuation of IP.

All AE data will also be listed, including separate lists for SAEs, AEs leading to death, and AEs leading to IP discontinuation. Listings will clearly indicate AEs to be treatment-emergent or not.

In addition, AEs related to SARS-CoV-2 will be listed separately.

6.3.1.9. EudraCT Adverse Events Reporting

For the purpose of EudraCT reporting, the following tabulations will be created:

Frequency tabulations, by system organ class and preferred term, of the number (percent) of subjects with non-serious TEAE will be presented. A similar table will be provided for all serious TEAEs, as well as a table for non-serious TEAEs reported in at least 2 subjects in any treatment group.

6.3.2. Laboratory Safety

6.3.2.1. Available Data

Laboratory tests scheduled are described in the protocol section 8.5.2. In addition, the derived laboratory tests described in Section [6.3.2.2](#) will be added.

The statistical analyses will only present results in Standard International (SI) standardized units. Other units will not be presented.

Only data provided by the central laboratory along with corrected calcium (mmol/L) will be used in tables and figures. Results from local labs will be listed only.

The parameter (hs)CRP will not be presented in this laboratory section of the analysis, but presented in the efficacy part.

6.3.2.2. Derivation Rules

Derived Laboratory Tests

The calcium level should be corrected in patients with low serum albumin levels, using the following formula:

Adjusted total calcium (mmol/L) = Total calcium (mmol/L) + 0.02 [40 - Albumin(g/L)]

Fasted and Non-Fasted Results

Laboratory tests that are sensitive to the fasting status: glucose, triglycerides.

For these laboratory tests, only results from blood samples drawn in a fasted state will be included in the analysis. Results from blood samples taken in a non-fasted (not fasting and fasting not declared) state will be listed only and no toxicities or abnormalities will be calculated. Laboratory results for which the fasting status is missing will be considered as taken non-fasted.

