8.5.2. Clinical Laboratory Evaluations

The following clinical laboratory safety tests will be performed:

- **Hematology:** hematocrit, hemoglobin, red blood cell count, white blood cell count, white blood cell differential count (absolute and relative), mean corpuscular volume (MCV), mean corpuscular hemoglobin (MCH), mean corpuscular hemoglobin concentration (MCHC), red blood cell distribution width and platelets.
- **Coagulation:** INR (only when increase in LFTs, see Section 6.4), activated partial thromboplastin time and prothrombin time.
- **Clinical chemistry:** glucose, urea, creatinine, uric acid, sodium, potassium, calcium, reflex calcium (free/ionized; only if serum calcium total is elevated), chloride, phosphorus, AST, ALT, GGT, total bilirubin, alkaline phosphatase (ALP, ALP fractions only if ALP is elevated), creatine phosphokinase, lipase, amylase, lactate dehydrogenase, insulin, hemoglobin A1c (HbA1c), albumin, total proteins, triglycerides, cholesterol, high-density lipoprotein (HDL), low-density lipoprotein (LDL), and hsCRP. Homeostatic model assessment of insulin resistance (HOMA-IR, see [Definition of Terms](#)) and HDL/LDL ratio will be derived from clinical chemistry parameters. An estimate of the

ClCr based on the serum creatinine level will be calculated by the central laboratory using the Cockcroft-Gault formula (see [Definition of Terms](#)).

– **Urinalysis:**

Dipstick: pH, glucose, proteins (qualitative), blood, leukocytes, ketones.

Microscopic examination of the sediment for cellular elements (cylinders, erythrocytes, leukocytes), if indicated (when the test strip was positive for blood and/or proteins).

Quantitative urine proteins, only when the test strip was positive for proteins.

Calcium, phosphate, creatinine and N-acetyl- β -D-glucosaminidase (NAG). The urine protein to creatinine ratio will be derived.

– **Serology:**

HBsAg and hepatitis C antibody, and HIV 1 and 2 (at screening). Positive hepatitis and HIV results should be reported by the investigator as required by local law.

– FSH test for females at screening to confirm menopause if applicable

– **Pregnancy test for females:**

serum beta human chorionic gonadotropin at screening, baseline (Visit 1), at Visit 4 (Day 29) and at Visit 5 (Day 43), , or the ED visit, if applicable (all female subjects).

– **QuantiFERON-TB Gold test** to check for latent or active TB (at screening). TB results should be reported by the investigator as required by local law.

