8.11. Schedule of Activities

For detailed instructions on the clinical study procedures, please see referred sections and Section 8.1, “[Timing of Assessments](#)”.

EVENT	SCREENING PERIOD	TREATMENT PERIOD ^{1,2}						FOLLOW-UP PERIOD ²
		1	2	3	4	5	ED ³	
Study visit	S	1						FU Visit
Study Weeks		Baseline	1	2	4	6		
Study Day (D) ± Days	-21 to -1	1	8 ± 2	15 ± 2	29 ± 2	43 ± 2	Early treatment discontinuation	57 ± 3
On site visit	✓	✓		✓	✓	✓	✓	✓
Telephone call			✓					
Informed consent	✓							
Inclusion/exclusion criteria	✓	✓						
Demographics	✓							
Medical history	✓							
FSH test (postmenopausal women)	✓							

¹ On dosing days, all assessments are to be performed within 3 hours pre-dose, unless otherwise specified.

² Subjects must come for the study visits 1, 3 and 5 in the morning in a fasting state (no food intake for at least 8 hours). For Visit 1 (predose measurements) and for 2 post dose visits (Visit 3, 4 or 5) all attempts should be made to plan the visit within 2 days following MTX intake.

³ Subjects who discontinue treatment early will be requested to return for an early discontinuation (ED) visit to complete all Visit 5 assessments and to return for a follow-up (FU) visit 14 ± 3 days after last IP administration.

EVENT	SCREENING PERIOD	TREATMENT PERIOD ^{1,2}						FOLLOW-UP PERIOD ²
		1	2	3	4	5	ED ³	
Study visit	S	1						FU Visit
Study Weeks		Baseline	1	2	4	6		
Study Day (D) ± Days	-21 to -1	1	8 ± 2	15 ± 2	29 ± 2	43 ± 2	Early treatment discontinuation	57 ± 3
Pregnancy test ⁴	✓	✓			✓	✓	✓	
Physical examination	✓	✓				✓	✓	✓
Vital signs	✓	✓		✓	✓	✓	✓	✓
Body weight and height ⁵	✓	✓		✓	✓	✓	✓	✓
12-lead triplicate ECG	✓	✓		✓	✓	✓	✓	✓
Serology	✓							
QuantiFERON-TB Gold test	✓							
SARS-CoV-2 RT-PCR test ⁶	✓	✓	As needed					
SARS-CoV-2 serology test ⁶		✓	As needed					
Randomization		✓						
Clinical safety blood samples	✓	✓ ⁷		✓ ⁷	✓	✓ ⁷	✓	✓

⁴ Serum beta human chorionic gonadotropin at screening, baseline (Visit 1), Visit 4 and Visit 5, or at the ED visit, if applicable (all female subjects).

⁵ Height only to be measured at screening.

⁶ RT-PCR from a nasal swab sample at screening and RT-PCR from a nasal swab sample and serology testing at baseline (Visit 1), and as needed when subject presents signs and symptoms of SARS-CoV-2 infection.

⁷ Fasted glucose, fasted insulin and HOMA-IR only at Visit 1, 3 and 5 and the ED visit, if applicable.

EVENT	SCREENING PERIOD	TREATMENT PERIOD ^{1,2}						FOLLOW-UP PERIOD ²

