6.5.2. Presentation of Results

All continuous parameters mentioned in section 6.5.1 will be summarized by means of descriptive statistics (including 90% CI of the mean change from baseline) by treatment group and analysis window. Actual values, changes from baseline and percent change from baseline will be tabulated separately.

Between-group comparisons will be based on the percent change from baseline, and will present a p-value and 90% CI of the delta between GLPG3970 and placebo. The same MMRM approach as for the efficacy endpoints will be applied.

Graphs of the mean (+- SE) actual values over time and of the mean (+- SE) change from baseline, and percent changes from baseline will be presented for all continuous parameters. Also, linear-linear plots for actual values will be provided by treatment group. In addition, profile line plots of the percent change from baseline will be provided by treatment group.

For cytokines and metabolic markers mentioned under section 6.5.1, the analysis of percent change from baseline will be performed as described in section 4.5.2. The same MMRM approach as detailed in [section 6.5.1.2](#) will be applied. The GeoLSM and GeoSE and corresponding 90 % CI will be presented (the same back transformation to the 'percentage scale' as for the geometric descriptive statistics will be applied to the LS-mean, SE and corresponding 90% CI bounds). The GeoMean (\cdot/\div GeoSE) of the actual values and percent changes from baseline will be presented graphically over time on a log-linear scale. Error band will be calculated as follows:

- Error bands: $100 \times [\text{exponential} \{ \text{mean} (Z) \pm \text{SE} (Z) \} - 1]$. Where $Z = \log (\text{value}) - \log (\text{baseline})$.

Listings will be provided for all cytokines, bone markers and metabolic markers separately. Column includes the actual values, change from baseline and percent change from baseline, and also a flag for high/low values in case a normal range exists.

Note: HOMA-IR values will be excluded from analysis if samples are not taken fasted (i.e. "fasted" is explicitly mentioned in the database),

6.6.

[REDACTED]

[REDACTED]

[REDACTED]

[REDACTED]

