Glucose (fasting)	<LLN	<55 mg/dL; <3.0 mmol/L	<40 mg/dL; <2.2 mmol/L	<30 mg/dL; <1.7 mmol/L	>ULN	>125 mg/dL; ≥6.95 mmol/L	>250 mg/dL; ≥13.89 mmol/L	≥500 mg/dL; ≥27.75 mmol/L
Glucose (non-fasting)	<LLN	<55 mg/dL; <3.0 mmol/L	<40 mg/dL; <2.2 mmol/L	<30 mg/dL; <1.7 mmol/L	>ULN	>160 mg/dL; ≥8.89 mmol/L	>250 mg/dL; ≥13.89 mmol/L	≥500 mg/dL; ≥27.75 mmol/L
HbA1c	NA	NA	NA	NA	>6.0	> 6.5 %	NA	NA
Fasting insulin	<2.6 µU/mL or 18.1 pmol/L	NA	NA	NA	>24.9 µU/mL or 172.9 pmol/L	NA	NA	NA
Cholesterol	NA	NA	NA	NA	>ULN	>300 mg/dL; ≥7.75 mmol/L	>400 mg/dL; ≥10.34 mmol/L	>500 mg/dL; ≥12.92 mmol/L
Low-density lipoprotein (LDL)	NA	NA	NA	NA	NA	≥160 mg/dL; ≥4.12 mmol/L	≥190 mg/dL; ≥4.90 mmol/L	NA

Parameter	L1	L2	L3	L4	H1	H2	H3	H4
High-density lipoprotein (HDL)	NA	<40 mg/dL; <1 mmol/L	NA	NA	NA	NA	NA	NA
Triglycerides	NA	NA	NA	NA	>ULN	>300 mg/dL; >3.42 mmol/L	>500 mg/dL; >5.7 mmol/L	>1,000 mg/dL; >11.4 mmol/L
Calcium (corrected for albumin)	<LLN	<8.0 mg/dL; <2.0 mmol/L	<7.0 mg/dL; <1.75 mmol/L	<6.0 mg/dL; <1.5 mmol/L	>ULN	>11.5 mg/dL; ; >2.9 mmol/L	>12.5 mg/dL; ; >3.1 mmol/L	>13.5 mg/dL; ; >3.4 mmol/L
Ionized calcium	<LLN	<1.0 mmol/L	<0.9 mmol/L	<0.8 mmol/L	>ULN	>1.5 mmol/L	>1.6 mmol/L	>1.8 mmol/L
Sodium	<LLN	<130 mEq/L; <130 mmol/L	<125 mEq/L; <125 mmol/L	<120 mEq/L; <120 mmol/L	>ULN	>150 mEq/L; >150 mmol/L	>155 mEq/L; >155 mmol/L	>160 mEq/L; >160 mmol/L
Chloride	<LLN	NA	NA	NA	>ULN	NA	NA	NA
Potassium	<LLN	NA	<3.0 mmol/L	<2.5 mmol/L	>ULN	>5.5 mmol/L	>6.0 mmol/L	>7.0 mmol/L
Phosphate	<LLN	<2.0 mg/dL; <0.65 mmol/L	<1.4 mg/dL; <0.45 mmol/L	<1.0 mg/dL; <0.32 mmol/L	>ULN	NA	NA	NA
Creatine phosphokinase (CPK)	NA	NA	NA	NA	> ULN	>2.5 x ULN	>5 x ULN	>10 x ULN
Uric acid	NA	NA	NA	NA	>ULN	≥10 mg/dL; ≥0.59 mmol/L	≥12 mg/dL; ≥0.71 mmol/L	≥15 mg/dL; ≥0.89 mmol/L
Albumin	<LLN	<30 g/L	<20 g/L	NA	NA	NA	NA	NA

Parameter	L1	L2	L3	L4	H1	H2	H3	H4
eGFR (or Cr/Cl)	<LLN	<60 ml/min/ 1.73 m ²	<30 ml/min/ 1.73 m ²	<15 ml/min/ 1.73 m ²	NA	NA	NA	NA
Blood urea nitrogen (BUN)	NA	NA	NA	NA	>ULN	>2.5 ULN	>5 ULN	>10 ULN

Table 3 Gradings for Urine Analysis Parameters

Parameter	L1	L2	L3	L4	H1	H2	H3	H4
Urine erythrocytes	NA	NA	NA	NA	≥ULN	≥10 cells/HPF	NA	NA
Urine protein	NA	NA	NA	NA	1+ proteinuria	2+ and 3+ proteinuria; urinary protein <3.5 g/24 hrs	urinary protein ≥3.5 g/24 hrs; 4+ proteinuria	NA
Urine glucose	NA	NA	NA	NA	>ULN (presence of glucose)	NA	NA	NA

LLN: lower limit of normal, ULN: upper limit of normal, NA: not applicable.

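### The SAP's fasted-sample rules cover glucose, triglycerides and HOMA-IR but not insulin, so non-fasted insulin is handled differently from glucose and HOMA-IR in the same sample (minor)

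*SAP*

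**What the plan says.** **Fasting rule.** SAP 6.3.2.2 names the tests it covers: "Laboratory tests that are sensitive to the fasting status: glucose, triglycerides". It continues: "For these laboratory tests, only results from blood samples drawn in a fasted state will be included in the analysis". For those tests, results from samples in a non-fasted "state will be listed only and no toxicities or abnormalities will be calculated". Missing status is settled too: "Laboratory results for which the fasting status is missing will be considered as taken non-fasted".

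**HOMA-IR.** The note closing SAP 6.5.2 says "HOMA-IR values will be excluded from analysis if samples are not taken fasted". Its parenthesis appears to require the fasted status to be explicit in the database. Insulin is not mentioned.

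**Insulin in the plan.**
- Protocol 8.5.2 lists it in the chemistry panel: "lactate dehydrogenase, insulin, hemoglobin A1c (HbA1c), albumin, total proteins".
- Protocol 8.11, footnote 7, schedules it: "Fasted glucose, fasted insulin and HOMA-IR only at Visit 1, 3 and 5 and the ED visit, if applicable".
- SAP 4.4.2 and footnote 16 to SAP 6.3.2.9 name fasted insulin as a metabolic marker. The footnote moves it out of the continuous laboratory summaries; SAP 6.3.2.9 sends those to the pharmacodynamic section.
- SAP Appendix I has one row for it, "Fasting insulin", with L1 below 2.6 and H1 above 24.9 µU/mL. Glucose has a fasting and a non-fasting row.

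**Tables that could receive the value.** SAP 6.3.2.4 assigns low, normal or high to all laboratory-provided tests. SAP 6.3.2.7 takes the worst case over all non-missing post-baseline records, unscheduled and follow-up visits included. SAP 6.5.2 compares arms on percent change from baseline by MMRM, on the log scale for metabolic markers, with p-values and 90% CIs.

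**The concern.** HOMA-IR is fasting insulin times fasting glucose divided by a constant. The SAP protects the product and one factor against non-fasted samples but leaves the other factor unprotected, without giving a reason. The gap also opens when the subject did fast but the status was not recorded. Glucose is then treated as non-fasted, HOMA-IR appears to be dropped, and insulin stays.

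Two things are at stake. First, a non-fasted insulin value could set a subject's worst-case abnormality class, or through Visit 1 the baseline class, in a table whose limits presume fasting. Second, the insulin and HOMA-IR comparisons could rest on different samples in a trial of 15 versus 10. If this is left open, someone must decide during analysis which insulin values count.

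**Working it through.** The plan states no figure on this point, so there is none to reproduce. The first check is textual.

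**1. One sample, non-fasted or with status missing, at Visit 1, 3, 5, ED or an unscheduled visit where insulin is run**

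| Result | Governing text | Outcome |
|---|---|---|
| Glucose, triglycerides | SAP 6.3.2.2 | listed only, no grade or abnormality |
| HOMA-IR | SAP 6.5.2 note | excluded from analysis |
| Insulin, low/normal/high class | SAP 6.3.2.4, 6.3.2.7, 6.3.2.9 | retained |
| Insulin, toxicity grade | SAP 6.3.2.3, Appendix I | apparently graded against the fasting limits |
| Insulin, summaries and MMRM | SAP 6.5.1 (redacted), 6.5.2 | retained unless 6.5.1 says otherwise |

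Footnote 16 removes insulin only from the continuous laboratory summaries, so it does not take insulin out of the abnormality tables.

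**2. The insulin limits themselves.** 18.1/2.6 = 6.96 and 172.9/24.9 = 6.94 pmol/L per µU/mL. The two unit versions agree; the limits are not in question.

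**3. Size of one fed value.** The documents give no food effect and no SD for insulin. Assume a fed value is k times the fasting value, with k = 3, 5 or 10, and a log-scale SD of change of 0.4. Arm sizes of 15 and 10 are the planned ones.

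Shift in one arm's geometric mean ratio to baseline from one fed post-baseline value: exp(ln k / n) − 1.

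| k | n = 15 | n = 10 |
|---|---|---|
| 3 | +7.6% | +11.6% |
| 5 | +11.3% | +17.5% |
| 10 | +16.6% | +25.9% |

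If each arm has one fed value, the net shift in the ratio of arms (active to placebo) is exp(ln k × (1/15 − 1/10)) − 1 = −3.6%, −5.2% or −7.4%.

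**4. Precision.** One value shifted by ln k raises the expected sample variance in its arm by (ln k)²/n. For k = 5, (ln 5)² = 2.590.
- Fed value in the 15-subject arm: SD = √(0.16 + 2.590/15) = √0.333 = 0.577, which is 44% above 0.40.
- Pooled SD with that arm affected: √[(14 × 0.333 + 9 × 0.16)/23] = 0.515, up 29%.
- Fed value in the 10-subject arm: arm variance 0.16 + 2.590/10 = 0.419; pooled SD = √[(14 × 0.16 + 9 × 0.419)/23] = 0.511, up 28%.

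**5. Could one value create a signal?** This uses a simple two-sample comparison at one visit in place of the MMRM, with no true effect and the fed value in the 10-subject arm.
- k = 5: shift ln 5/10 = 0.161; SE = 0.511 × √(1/15 + 1/10) = 0.209; t = 0.77.
- k = 10: shift 0.230; arm variance 0.16 + 5.302/10 = 0.690; pooled SD 0.606; SE 0.247; t = 0.93.
- Two-sided 10% critical value on 23 df: about 1.71.

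The expected statistic stays well short of significance. What remains is the loss of precision in step 4.

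**The case against.** The strongest reply is that the insulin analysis belongs to SAP 6.5, whose first subsection is blacked out. The version history shows that 6.5.1 deals with fasting insulin, so a fasting rule may sit there, and a note about HOMA-IR does not prove otherwise. This stands for the summaries and the MMRM, and that part of the point is conditional.

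The parameter is also labelled fasted insulin, so a fed value is arguably not that parameter at all. SAP 4.3.8, which keeps all measured values, is about outliers and does not admit fed samples. Both remarks are fair. But glucose also appears under a fasted label and still has an explicit rule, and a label does not settle samples with missing status.

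On grading, SAP 6.3.2.3 grades only tests for which grades exist, and Appendix I has no non-fasting insulin row. Non-fasted insulin could therefore be read as ungraded. No text says so, hence apparently graded. The low/normal/high classification does not depend on that row.

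A reader might infer that Visit 4, follow-up or screening samples also feed non-fasted insulin into the analysis, since insulin is in the general chemistry panel. The documents do not support this: footnote 7 confines fasted insulin to Visits 1, 3, 5 and ED, and nothing schedules a separate non-fasted insulin.

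A reader might also infer that one fed sample could produce a false metabolic finding. The assumed figures do not bear this out, and fed samples in both arms partly offset each other.

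Exposure is limited as well: a fast of at least 8 hours is required at every visit where fasted insulin is scheduled.

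**Conclusion.** The inconsistency is real and visible in unredacted text: the fasted-sample rules reach glucose, triglycerides and HOMA-IR, and insulin is left out. Retention in the low/normal/high tables follows from that text. Retention in the Appendix I grading is the apparent reading. Retention in the summaries and MMRM holds only if SAP 6.5.1 has no insulin rule.

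The consequence is minor. Insulin is neither the primary nor a secondary endpoint and plays no part in the decision framework. Its Appendix I grading stops at L1/H1, so it cannot reach the grade 2 threshold for a marked laboratory abnormality. The issue needs a departure from the fast or a missing fasting flag. On an assumed 5-fold fed value in one arm, that arm's geometric mean ratio moves by about 11% (n=15) or 17% (n=10). With an assumed log-scale SD of 0.4, the pooled SD rises by just under 30%. Both the fold change and the SD are assumptions. The main harms are lost precision and insulin and HOMA-IR resting on different samples.

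**What to change.** In SAP 6.3.2.2, change the list to: glucose, insulin, triglycerides. In the SAP 6.5.2 note, change HOMA-IR to: Insulin and HOMA-IR. State that insulin from a non-fasted sample, or one with undeclared fasting status, is listed only and neither graded nor classified. If SAP 6.5.1 already holds an insulin rule, a cross-reference from 6.3.2.2 would do for the continuous analyses, but the abnormality tables still need the added word. Make the change before unblinding.

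The cost is a few words, using the fasting status that the SAP already relies on for glucose and HOMA-IR. The downside is that a few insulin values move to listings, including some from subjects who fasted but whose status was not recorded.
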